### 1.1 Background

Necrobiosis lipoidica (NL) is a chronic, disfiguring, relapsing-remitting inflammatory disease primarily involving the lower extremities. NL disproportionately afflicts younger patients and is classically associated with diabetes mellitus (DM). Clinically, NL presents with atrophic yellow telangiectatic plaques that ulcerate in 30% of patients.

Although multiple therapies have been used to treat NL lesions, experience is largely anecdotal and there is paucity of data to guide effective treatment. Topical, intralesional, and systemic corticosteroids have been effective in a small number of non-DM patients; however, corticosteroids are high-risk treatment option in diabetic patients because they increase blood glucose levels and promote insulin resistance. Various non-steroidal immunosuppressants have been used, including methotrexate, tumor necrosis factor alpha inhibitors, mycophenolate mofetil, and fumaric acid esters, all with mixed success. Better treatment options with acceptable risk/benefit profile are clearly needed.

To characterize NL at the molecular level, we performed RNA sequencing to identify underlying immune mechanisms and possible therapeutic targets. We sequenced 18 representative NL tissues and 5 normal skin tissues, and identified deregulated genes enriched for immune system functions. Independent validation was performed using a Nanostring expression panel (594 immune-specific genes), demonstrating high concordance in the set of genes identified as differentially expressed by both platforms. Upregulated immunologic processes/pathways included those involved in T-helper cell induction, dendritic cell maturation, macrophage stimulation, and autoimmunity, indicating diverse immunological pathways are active in NL.

Importantly, we focused on identifying targetable “drivers” of downstream RNA expression changes. We prioritized such driver genes using by querying multiple drug databases in order to identify clinically targetable drivers. Using stringent criteria, we identified JAK1/2 and IFN $\gamma$  as key, activated drivers, and ruxolitinib as one of the most highly rated potential therapeutics in this search.

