#### 1.4 Clinical Data to Date

Plasma concentrations of ruxolitinib cream were determined following topical application of ruxolitinib cream in plaque psoriasis, AA, AD, and vitiligo, mostly using sparse sampling. The exposures of ruxolitinib were generally strength-dependent with moderate intersubject variability.

In Study INCB 18424-201 in plaque psoriasis, the observed systemic bioavailability of ruxolitinib was independent of formulation strength.

In Study INCB 18424-202 in plaque psoriasis, an intensive sampling scheme was used on the last day of treatment to better characterize the PK following topical application. The systemic PK following topical application was characterized by apparent first-order release, modest peak-to-trough excursion (ratio ~2), estimated relative bioavailability of 3% to 5%, and an  $t_{1/2}$  of approximately 3 days. Systemic bioavailability of ruxolitinib cream was shown to be independent of the strength of the cream formulation and %BSA. The PD results from skin biopsies, including markers for Th1, Th17 pathway activation, reduced levels of inducible nitric oxide synthase, and KRT16 transcript levels, suggest that ruxolitinib cream was pharmacologically active at a local but

not systemic level when administered to participants with active psoriasis for 28 days as either a QD or BID regimen and suggest that key pathologic pathways in the psoriatic lesion are favorably impacted by treatment with ruxolitinib cream.

In Study INCB 18424-204 in AA, ruxolitinib trough concentrations increased as percentage scalp involvement increased.

In Study INCB 18424-206 in AD, trough plasma concentrations increased as the strength of ruxolitinib cream and frequency of applications increased. Participants whose plasma concentrations exceeded 125 nM (equivalent to half of the IC50 value based on the effect of ruxolitinib on IL-6) tended to have more extensive skin involvement and highly inflamed AD lesions. However, no correlation was observed between higher ruxolitinib blood levels in these participants and their response to treatment.

In Study INCB 18424-102 in AD patients, steady-state plasma concentrations (based on geometric mean) following BID administration of 1.5% ruxolitinib cream in adolescent participants were similar to that in adult participants.

In Study INCB 18424-211 in vitiligo, plasma concentrations of ruxolitinib increased as the strength and frequency of application of the cream were increased.

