**Exploratory Objectives:**

To predict responses and examine the pharmacodynamics of treatment through the identification of unique biomarkers and transcriptomic changes of NL at week 0 and utilizing RNA sequencing on responsive and non-responsive tissue at week 4 To correlate these biomarkers with measures of global response: NL Lesion Score, PGA, and BSA.

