Tissue will be collected for RNA sequencing at week 0 and 4. Blood collection will include the isolation at week 0, 2, 4, 8, 12. 5mL vials of blood which will be separated and the serum and cell

pellet will be stored for future analysis. Three skin biopsies will be taken during the study. At week 0, one 3mm tissue biopsy will be taken from lesional skin and one biopsy will be taken from non-lesional (adjacent but normal-appearing a minimum of 2 cm from the primary lesion but within the same anatomical subunit) skin. At week 4, a 3mm biopsy will be taken from a treated lesion (Ideally the same lesion as the initial biopsy, separated by a minimum of 1cm, or a similar lesion in the same anatomical subunit). The lesions will be chosen using full body photographs taken at week 0. From the biopsy specimen, a small piece of tissue (approximately 1 mm) will be cut and placed in a bottle labeled for RNAseq. The larger specimen will be placed in a bottle labeled for biobank storage. Both samples will be snap frozen and stored in the biobank. Once sample collection is completed for all samples, the tissues labeled for biobank storage will continue to be stored in the biobank and RNA sequencing will be performed on the tissue samples labeled for RNAseq (up to 36 tissue samples) and analysis will be performed. Paired analysis of treatment responsive and refractory lesions will be made as well as treated and untreated lesions.

**Nucleic Acid Extractions:** RNA will be extracted from a total of 50 um of fresh tissue using the Qiagen FFPE RNeasy Micro extraction Kit according to manufacturer's recommendation.

**RNA Transcriptome Sequencing:** RNA transcriptome sequencing will be carried out using commercially available techniques. Briefly, RNA libraries will be created using up to 100ng of RNA as starting material using the Illumina RNA TruSeq Library kit according to manufacturer's recommendation. Libraries will be QCed for quality and quantity using the Illumina TapeStation High Sensitivity tape. Paired-end sequencing will then be carried out on the Illumina HiSeq 4000 using 101bp insert fragments.

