### **3.2 Number of Subjects**

12 subjects will be enrolled in this study.

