## 7.2 Statistical Methods

### Descriptive Statistics

#### Sample Size Computation and Power Analysis:

The sample size for this pilot study is set at 12 subjects for logistical and financial reasons. This is similar in size to other exploratory studies and will provide adequate data for estimation purposes for planning future studies. With 12 subjects, the study is intended to be for estimation purposes only.

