### Bioinformatic Analysis:

RNA-seq analysis: We will use our recently developed LinNorm program

to process RNA-seq data and detect differentially expressed genes (DEGs) by comparing the RNA-seq profiles. We will first find DEG between responsive and non-responsive samples from the same individual by using paired or unpaired Wilcoxon rank-sum test (depending on how the samples are collected). We will then rank each gene in the DEGs based on the occurrence frequencies in all 12 subjects to find common DEGs for responsiveness (use permutation test to determine the p value). By comparing the normal tissue with the pathogenic tissue (responsive + non-responsive) using the above approach, we will detect a common DEGs for NL pathogenesis. Hierarchical clustering and Principal Component Analysis (PCA) will be applied to samples for their hierarchical relationship and clustering properties. Ideally normal, responsive and non-responsive tissues should form three distinct groups. The PCA analysis will provide us a set of gene signatures that can distinguish these three types of tissues. The common DEGs for responsiveness and pathogenesis, as well as gene signature from PCA will be used for our pathogenesis or survival

prediction. Additionally, we will perform de-convolutional analysis, to compare the immune profiles of responsive and non-responsive tissue and to correlate immune profiles. Predictive biomarkers will be correlated with lesional and global responses.

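### The contrast for NL pathogenesis genes puts drug-treated lesions in the disease group, although untreated Day 0 lesional and non-lesional pairs are collected

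*Combined protocol and SAP*

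**What the plan says.** Section 7.2, Bioinformatic Analysis, first looks for genes that differ between responsive and non-responsive samples. It then derives the pathogenesis genes "By comparing the normal tissue with the pathogenic tissue (responsive + non-responsive) using the above approach". That sentence names no visit for either tissue. The clustering and principal component (PCA) text uses the same three labels: "Ideally normal, responsive and non-responsive tissues should form three distinct groups".

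The timing has to come from other sections:

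- Section 2, Exploratory Objectives, speaks of "utilizing RNA sequencing on responsive and non-responsive tissue at week 4".
- The Study Summary (Objectives) and the Exploratory Outcome Measures in Section 3.1 place the same tissue at week 12.
- Section 3.1 schedules one lesional and one non-lesional biopsy at week 0, and then: "At week 4, a 3mm biopsy will be taken from a treated lesion". Table-2 and Sections 6.2 and 6.6 agree. No biopsy is scheduled at week 12.
- Section 3.1 has every lesion treated twice daily from the start. It also announces a paired analysis of treated against untreated lesions, which Section 7.2 does not take up.

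**The concern.** A disease signature should compare diseased with healthy tissue under otherwise equal conditions. Here the healthy sample precedes treatment, and the diseased sample, wherever the documents date it, follows weeks of the study drug. The difference then contains disease, drug effect and elapsed time together.

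The protocol itself gives reason to expect a drug effect. On the drivers of NL, Section 1.1 says "Using stringent criteria, we identified JAK1/2", together with interferon gamma, as key and activated. Section 1.4 reports that biopsy markers in psoriasis after 28 days of this cream suggest that "key pathologic pathways in the psoriatic lesion are favorably impacted by treatment with ruxolitinib cream". A gene that the drug moves towards normal would shrink in the disease list or fall out of it. A gene that the drug induces, unrelated to NL, could enter. Section 7.2 then uses the lists for prediction, and Section 7.1 gives predictive biomarkers as a reason for the design.

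**Working it through.** **1. Sample count.** Section 3.2: "12 subjects will be enrolled in this study". Section 3.1 gives three biopsies per subject: Day 0 lesional, Day 0 non-lesional and week 4 treated lesion. 12 × 3 = 36, which reproduces the stated maximum of 36 tissue samples. They split into 12 of each kind.

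**2. What the disease group can contain.**

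| Reading of responsive + non-responsive | Samples | Drug-exposed |
|---|---|---|
| Week 4 tissue (Section 2) | 12 week 4 | 12 of 12 |
| Week 12 tissue (Study Summary; Exploratory Outcome Measures) | none scheduled | would all be exposed |
| All lesional tissue, pooled | 12 Day 0 + 12 week 4 | 12 of 24 |
| Day 0 lesions labelled by later outcome | 12 Day 0 | 0 of 12 |

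Only the last reading keeps the drug out. No section states it, and it conflicts with each place where this tissue is dated.

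**3. Effect on the estimate.** Let D be a gene's log fold change, untreated lesion against normal skin, and let the drug remove fD by week 4.

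- Week 4 only: D − fD = (1 − f)D.
- Equal pooling: [D + (1 − f)D] / 2 = (1 − f/2)D.
- Gene with D = 0 that the drug shifts by e: the contrast gives e, or e/2 if pooled.

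The documents give no f, so the whole range is shown:

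| f (assumed) | 0 | 0.25 | 0.50 | 0.75 | 1 |
|---|---|---|---|---|---|
| Share of D retained, week 4 only | 1 | 0.75 | 0.50 | 0.25 | 0 |
| Share of D retained, pooled | 1 | 0.875 | 0.75 | 0.625 | 0.50 |

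**4. What that does to detection.** The plan has no alpha or power to reproduce: "With 12 subjects, the study is intended to be for estimation purposes only". As an illustration only, take 12 pairs, normally distributed differences with SD 1, an exact two-sided Wilcoxon signed-rank test at 0.05 and 20,000 simulations, for a single gene before any multiplicity adjustment. Week 4 tissue alone forms the disease group.

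| f (assumed) | 0 | 0.25 | 0.50 | 0.75 | 1 |
|---|---|---|---|---|---|
| Power, D = 1.0 SD | 85% | 61% | 32% | 11% | 4% |
| Power, D = 1.5 SD | 99% | 93% | 61% | 19% | 4% |

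A gene with no disease difference, shifted by the drug by 0.5 SD or 1.0 SD, would be flagged as a disease gene 32% or 85% of the time.

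**5. With Day 0 tissue on both sides.** The contrast uses 12 + 12 = 24 of the 36 planned samples as 12 same-day, untreated pairs. It estimates D whatever f is.

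**The case against.** The strongest reply is that the Section 7.2 sentence names no week. Responsive plus non-responsive may simply mean all lesional tissue, and Day 0 lesions could carry a label from the subject's later outcome. The aim of predicting response from week 0 biomarkers needs labels of that kind. This stands to the extent that a reader might infer that the 12 Day 0 lesional samples are left out of the contrast, and the text does not establish that. But pooling still puts treated tissue in the disease group, and the reading that avoids it is written nowhere.

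Three further replies hold against stronger readings:

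- A reader might infer that disease and drug effects cannot be separated in this trial. They can. Section 3.1 plans a treated-against-untreated comparison, and since all lesions are treated, the untreated ones must be the Day 0 biopsies. The samples exist; the Section 7.2 contrast does not use them to separate the two effects.
- A reader might infer that clustering and PCA omit untreated lesions. The three-group sentence states a hoped-for result and does not select samples. The remaining gap is that untreated lesion has no label of its own.
- A reader might expect the JAK and interferon genes to be lost. That is extrapolation. The Section 1.4 evidence concerns psoriasis and is worded as suggestive. Section 2 notes that the single NL case, on systemic drug, required 3 months, so f at week 4 may be small. Section 1.1 reports that those drivers came from a separate set of 18 NL and 5 normal tissues.

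The objection that this is one exploratory analysis in a 12-subject estimation study is correct. It limits the weight of the point without removing it.

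**Conclusion.** The point holds. On the most direct reading, the pathogenesis contrast compares Day 0 normal skin with lesions after about 4 weeks of ruxolitinib; on the pooled reading, half of the disease group is treated. Either way the drug effect enters the disease signature. The contrast retains (1 − f) of a gene's disease effect, or (1 − f/2) if pooled equally, and can list drug-induced genes as disease genes.

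The conclusion rests on reading the tissue labels through Section 2 and the biopsy schedule. The direction follows from the design for any gene that the drug affects. The size does not: f is unknown, and the power figures are illustrations under assumed values. The primary endpoint and the safety analyses are untouched. It is still more than an unstated detail, because the comparator as written would give a worse answer than one the trial already collects.

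**What to change.** In Section 7.2, Bioinformatic Analysis:

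1. Define the pathogenesis contrast as Day 0 lesional versus Day 0 non-lesional, paired within subject (up to 12 untreated pairs). Run the paired test across subjects. With one sample of each kind per subject, a rank-sum test inside one individual cannot give a two-sided p value below 1.
2. Carry over the comparison already announced in Section 3.1, stated as week 4 lesional versus Day 0 lesional, paired within subject. This is the pharmacodynamic contrast.
3. Label Day 0 lesional tissue as its own group in clustering and PCA.
4. State the visit for each tissue label, and reconcile the week 4 and week 12 wording in the Study Summary, the Exploratory Objectives and the Exploratory Outcome Measures with the biopsy schedule.

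The cost is analysis wording only: no new biopsy, visit or sequencing beyond the 36 samples planned. The change should be made before the sequencing data are analysed.

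### The within-subject Wilcoxon method in section 7.2 cannot call any gene from the planned biopsies, and the Week 4 versus Day 0 lesional contrast named in section 3.1 is not carried into it

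*Combined protocol and SAP*

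**What the plan says.** The Exploratory Objectives in section 2 set the aim: "To predict responses and examine the pharmacodynamics of treatment through the identification of unique biomarkers and transcriptomic changes of NL at week 0", with RNA sequencing of tissue at week 4.

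Section 3.1 fixes the tissue. "At week 0, one 3mm tissue biopsy will be taken from lesional skin and one biopsy will be taken from non-lesional" skin. "At week 4, a 3mm biopsy will be taken from a treated lesion", ideally the lesion sampled first, otherwise a similar one in the same anatomical subunit. Up to 36 tissue samples are to be sequenced. The same section says that every lesion is treated, and it promises: "Paired analysis of treatment responsive and refractory lesions will be made as well as treated and untreated lesions". It gives no test, time points or error control for that promise.

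Section 7.2, Bioinformatic Analysis, is where the RNA-seq tests are set. It names two differential-expression contrasts:

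- Responsive against non-responsive samples within the same individual, by a paired or unpaired Wilcoxon test. Genes are then ranked by how many of the 12 subjects show them, with a permutation p value.
- Disease against normal: "By comparing the normal tissue with the pathogenic tissue (responsive + non-responsive) using the above approach".

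Clustering, principal components and deconvolution follow, using the same tissue classes. Time point and treatment status do not appear in this part of the plan.

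**The concern.** There are two linked problems.

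First, the stated test works inside one person, and a person contributes one sample of each kind. A rank test needs replicates on at least one side before it can separate anything. If no gene can be called within a subject, there is nothing to count across subjects and nothing for the permutation step to rank.

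Second, the drug-effect question is part of the exploratory objective and section 3.1 names the comparison that answers it, but the section that sets the methods leaves it out. A related ambiguity is that section 7.2 pools responsive and non-responsive tissue as diseased tissue without saying whether treated Week 4 samples are included. If they are, the treatment effect is mixed into the disease signature.

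What is at stake is the credibility of the transcriptomic results. With the written method unusable, the contrast, the model and the error control would all be chosen after the data are in hand, over a very large number of genes.

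**Working it through.** **Inputs**

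- Subjects: 12 (section 3.2: "12 subjects will be enrolled in this study").
- Tissue per subject: Day 0 lesional 1, Day 0 non-lesional 1, Week 4 treated lesional 1 (sections 3.1, 6.2 and 6.6).
- Withdrawals are not replaced (section 4.4.1), so 12 pairs is a ceiling.
- Genes tested: not stated for this trial. I show 594, the size of the panel used in the earlier work (section 1.1), and 20,000 as an assumption.
- False discovery rate: none is stated. 5% is assumed.

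**The plan's own figure.** 12 subjects × 3 biopsies = 36, which reproduces the stated maximum. The design therefore yields at most 12 Day 0/Week 4 lesional pairs.

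**The within-subject test.** The smallest exact two-sided p is min(1, 2/C(n1+n2, n1)) for the rank-sum test and min(1, 2/2^n) for the signed-rank test on n pairs.

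- One sample against one, rank-sum: 2/C(2,1) = 2/2 = 1.
- One pair, signed-rank: 2/2^1 = 1.
- One normal sample against two lesional samples (Day 0 and Week 4 pooled): 2/C(3,1) = 2/3 = 0.667.

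At any threshold below 0.667, no gene is called in any subject under either listed contrast. Every gene has a count of zero, so the frequency ranking is empty. For responsive against non-responsive there is a further difficulty. Only one treated lesion per subject is biopsied, so a subject normally supplies only one of the two classes.

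**The same samples analysed across subjects.** With one Week 4 minus Day 0 difference per subject and gene, 12 pairs give a smallest signed-rank p of 2/2^12 = 2/4096 = 0.00049. The contrast is therefore feasible.

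**How coarse a plain signed-rank test would be.** Benjamini-Hochberg declares k genes only if the k-th smallest p is at most k × 0.05/m. No p can lie below the floor, so k must be at least floor × m/0.05, rounded up.

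| Pairs | Smallest p | Fewest discoveries, m = 594 | Fewest discoveries, m = 20,000 |
|---|---|---|---|
| 12 | 0.00049 | 6 | 196 |
| 10 | 0.00195 | 24 | 782 |
| 8 | 0.0078 | 93 | 3,125 |

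For 12 pairs and 20,000 genes: 0.000488 × 20,000/0.05 = 195.3, so 196. These are minimum totals of discoveries. They need not all have the smallest p: the next attainable value is 4/4096 = 0.000977, and 391 genes at that value would also pass, since 391 × 0.05/20,000 = 0.0009775.

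**The case against.** The strongest reply is that the pre/post contrast is not missing from the protocol. Section 3.1 promises it, section 1.1 plans sequencing before and after treatment, and the general part of section 7.2 offers paired Wilcoxon tests for numerical outcomes, which could be run across subjects. This stands in part. A reader might infer that the protocol never planned the comparison, or that 12 pairs would go unused; the documents do not support either. But the line in section 3.1 has no method attached. The general Wilcoxon sentence is generic and has no rule for thousands of genes, and the RNA-seq part sets its own, different procedure.

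A second reply is that the per-subject approach is assigned to the two listed contrasts and not to pre/post. That is correct. The failure shown above is a failure of those listed contrasts; it would extend to pre/post only if the approach were reused there.

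A third reply is that the plan names a software program for detecting differential expression and leaves pairing open. Both pairing options were checked and neither gives p below 1 for one sample against one. The text describes no other test that the program would apply.

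Finally, the trial's purpose is modest: "With 12 subjects, the study is intended to be for estimation purposes only". The objective is exploratory, and the outcome-measures text qualifies the biomarker correlation as dependent on the data. This limits the severity. It does not rescue a method that cannot return a result, and within-subject rank tests do not supply the effect estimates that an estimation study needs.

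**Conclusion.** The point holds in this form: the only differential-expression test that section 7.2 states fails with the planned biopsies (smallest p of 1, or 0.667 if both lesional samples are pooled), and the treated-versus-untreated contrast named in section 3.1 is not specified there. The first part rests only on the biopsy counts and the stated test. The multiplicity figures rest on the assumed 5% rate and the assumed gene counts. They show that a plain signed-rank test across subjects is usable but coarse: at least 196 discoveries to declare any over 20,000 genes, but only 6 over 594.

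Three stronger readings are tempting and should not be drawn:

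- Pre/post change is not the only question the biopsies serve. The objective puts prediction of response first, and the non-lesional biopsy serves the disease contrast.
- It is not required that 196 genes all sit at the minimum p; that number is a minimum total.
- No primary or secondary endpoint is touched.

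This is a change that should be made before sequencing data are analysed. It does not threaten the trial.

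**What to change.** In section 7.2, Bioinformatic Analysis:

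1. Replace the within-individual Wilcoxon test and frequency ranking with gene-wise contrasts fitted across subjects, using a linear or negative-binomial model with variance shared across genes. Use subject as blocking factor for the within-subject contrasts. Responder status varies between subjects, so treat it as a between-subject factor.
2. Add Week 4 minus Day 0 lesional tissue, paired by subject. State that there are at most 12 pairs, and that pairing is by subject because the Week 4 lesion may be a similar one.
3. State that the normal-versus-lesional disease contrast uses Day 0 tissue only.
4. Control the Benjamini-Hochberg false discovery rate at a stated level, for example 5%. Report log fold changes and the number of pairs in each contrast.
5. Reconcile the timing of tissue sequencing. The Study Summary and the Exploratory Outcome Measures say week 12; the Exploratory Objectives, section 3.1, Table-2 and section 6.6 say week 4.

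The cost is a paragraph of text and a little analysis work, with no new visits, biopsies or samples. Section 3.1 has sequencing start only after all samples are collected. The small downside is a model assumption in place of a rank test.

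### The plan promises that PCA will yield gene signatures for responsive and non-responsive tissue and uses them for prediction, with no check that they separate the tissues and with a survival target the trial does not have

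*Combined protocol and SAP*

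**What the plan says.** Section 2 sets the exploratory objective: "To predict responses and examine the pharmacodynamics of treatment through the identification of unique biomarkers". Under Bioinformatic Analysis in section 7.2 the plan describes two routes to a gene list.

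- **DEG route.** Responsive and non-responsive samples are compared by Wilcoxon tests and genes are ranked by how often they recur across subjects, to "find common DEGs for responsiveness (use permutation test to determine the p value". Normal and diseased tissue are then compared by the same approach.
- **PCA route.** Hierarchical clustering and PCA "will be applied to samples for their hierarchical relationship and clustering properties". The expectation is that "Ideally normal, responsive and non-responsive tissues should form three distinct groups". The next sentence drops the hedge: "The PCA analysis will provide us a set of gene signatures that can distinguish these three types of tissues".

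Both products go forward together: the common DEGs "as well as gene signature from PCA will be used for our pathogenesis or survival" prediction. The part closes with "Predictive biomarkers will be correlated with lesional and global responses". On sample size, section 7.2 says "With 12 subjects, the study is intended to be for estimation purposes only".

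**The concern.** PCA finds directions of greatest total variance in the expression matrix. As described, neither the tissue label nor the clinical response is an input. Its loadings are therefore not response signatures unless someone shows that the component scores differ by response. The plan sets no such requirement. It does not say which genes enter, which components or loadings count, what degree of separation is needed, or what happens if the three groups do not form.

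The trial could therefore report a PCA gene list as predictive of response when nothing distinguishes it from a list obtained with no response signal at all. Section 7.1 justifies the small single-arm design partly by the predictive biomarkers it will yield, so this bears on what may be concluded.

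The prediction target is also wrong for this trial. No objective or endpoint in sections 2, 3.4 or 3.5 concerns survival. The documents touch on it only as vital status after a revoked authorisation (section 9.1) and in the forms that record death.

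**Working it through.** **1. Inputs from the protocol.** There are 12 subjects (section 3.2). Section 3.1 gives two biopsies per subject at week 0 (one lesional, one non-lesional) and one from a treated lesion at week 4. Total: 12 × (2 + 1) = 36, which reproduces the stated maximum of 36 tissue samples. Treated samples: 12 × 1 = 12. With one treated lesion per subject, responsive versus non-responsive treated tissue can only be a between-subject contrast in at most 12 samples.

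**2. Inputs not in the protocol.** Number of genes, responder split, variances, effect sizes and number of components are not given. All are assumed below.

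**3. No gene related to response.** Assumptions: 36 samples; 2,000 genes; a lesional-versus-normal effect in 10% of genes; subject SD 0.5; residual SD 1; 1,000 runs per responder split. Component scores of the 12 treated samples were compared by exact two-sided Mann-Whitney tests. The reference is 1 − 0.95^k for k independent tests.

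| Any of the first k components at p<0.05 | 3/9 split | 4/8 split | 6/6 split | 1 − 0.95^k |
|---|---|---|---|---|
| k = 1 | 3.6% | 6.1% | 5.2% | 5.0% |
| k = 2 | 7.2% | 10.6% | 9.7% | 9.8% |
| k = 3 | 10.8% | 14.7% | 14.0% | 14.3% |
| k = 5 | 17.0% | 23.1% | 20.3% | 22.6% |
| k = 10 | 34.5% | 46.8% | 39.7% | 40.1% |

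Loadings were returned in 100% of runs. The list always exists, while its relation to response is at chance level and grows only with the number of components inspected.

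**4. Two ways to get apparent separation from nothing.**

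- *Many components.* An intercept plus 11 component scores is 11 + 1 = 12 coefficients for 12 treated samples, enough to fit any labelling. Separation was perfect in 100% of null runs.
- *Preselected genes.* PCA was run on the 100 genes that differed most by response in the treated samples. The first component separated the groups completely in 100% of null runs at all three splits. This is circular.

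**5. When response genes do exist.** Assumptions: 36 samples; 5,000 genes; 2% response genes; 6 of 12 subjects responding; several combinations of between-subject and lesion variance. The table gives the share of true response genes among the top 100.

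| Response effect (log units) | By PCA loading | By ranking on response |
|---|---|---|
| 0 | about 2% (base rate) | – |
| 0.5 | 1–3% | 4.5–6.0% |
| 1 | 2–11% | 13–25% |
| 2 | 4–73% | 44–69% |

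With 10% response genes instead of 2%, PCA loadings gave 17–30% at effect 1 and 57–94% at effect 2, against a 10% base rate.

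**6. Existing safeguards.** The permutation p value sits in the DEG route. The closing correlation with response uses the same 12 subjects, and no cross-validation, hold-out or independent set is described. Neither tests whether the PCA components separate the tissues.

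**The case against.** The strongest defence has four parts.

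- **A label-based analysis is already planned.** This stands. The DEG route uses response, has a permutation p value and goes forward in the same sentence as the PCA signature. A reader might infer that true response genes will be lost because they load weakly on the leading components. The documents do not support that: a low loading removes no gene from the DEG list.
- **The plan does not say that all genes enter the PCA.** This also stands. PCA follows the DEG steps in the text and might be run on DEGs, so response could enter indirectly. That reading replaces an uninformative list with a circular one (step 4) and does not rescue the promised signature.
- **That loadings always exist is close to a truism.** This is fair. A reader might infer that a false split by response is certain. It is not: on the first two or three components it occurs in about 7% to 15% of null runs. The defect is that no rule tells a list with signal from one without.
- **The work is exploratory.** It is, section 3.1 makes the correlation with global response conditional on the data, and no primary, secondary or safety conclusion depends on it. That lowers the stakes. It does not justify an unconditional promise that the signature will distinguish the tissues.

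**Conclusion.** The point holds in limited form. The plan presents an unsupervised output as a signature distinguishing responsive from non-responsive tissue, attaches no separation check or permutation test to it, and uses it for prediction with a target that includes an outcome outside the trial's endpoints. The consequence is an unsupported additional signature that may be reported as predictive.

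Two results do not depend on the simulation settings: loadings exist under any data, and 11 components with an intercept can fit any labelling of 12 samples. The rest depends on assumed gene counts, variances and splits. A reader might infer that choosing genes by PCA is close to random in general. That is supported only for absent or weak response effects, and at an effect of 1 log unit only in some settings; with large effects PCA can recover response genes, over a wide range (4% to 73% at 2 log units with 2% response genes). Nor is the alternative strong for weak effects: ranking on response reached only 4.5% to 6.0% at 0.5 log units.

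This should be corrected, but it does not touch the primary analysis.

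**What to change.** In the Bioinformatic Analysis part of section 7.2:

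1. State that PCA and hierarchical clustering are for quality control and display only.
2. Delete the sentence promising distinguishing signatures from PCA.
3. Remove the PCA gene signature and the word survival from the prediction step.
4. Base any response signature on the label-based comparison with its permutation p value, permuting response labels between subjects, because only one treated lesion per subject is biopsied. One option, not the only one, is to relate Day 0 lesional expression to the same subject's change in NL score from Week 0 to Week 12.
5. Label the result hypothesis-generating.

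The cost is wording and one analysis step on samples already planned; no visits, tissue or subjects are added. The downside is that any signature from 12 subjects will be unstable. Permutation is also coarse for a responder split. At 6/6 there are C(12,6) = 924 labellings, so the smallest two-sided p is 2/924 = 0.0022. At 3/9 there are C(12,3) = 220, so the smallest p is 1/220 = 0.0045.
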